### **2.5.3 Outcome Components**

The results of the structure and the process are in the Donabedian model. Therapeutic options include outcomes as well as the beliefs, confidence, and knowledge of mothers and nurses related to health care (Donabedian, 1996, 2005). In this study, the effects of the KC-EP are measured at different phases of the study in relation to the outcomes of the mother-infant dyads and nurses. The results for mother-infant dyads and nurses will be measured by their personal satisfaction when attempting to implement KC, such as perception, knowledge, level of confidence regarding the initiation of KC with premature infants with monitoring devices, confidence level to initiate KC with premature infants with ventilator support and perceived barriers toward KC implementation which reflect personal beliefs, satisfaction, feelings and thoughts related to KC.

[figure not shown]

Figure 2.2: Conceptual Framework of Study from the Admission Day, Discharge And Follow-Up at 3 Months Old.

## 2.6 Conclusion

The literature suggests setting KC performance goals and using standardized guidelines and protocols for KC. However, to ensure success in the implementation of KC, the literature also emphasizes the need for the proper training of nurses and mothers.

Based on the literature review, it was noted the intervention studies focused on the outcomes measured in a unilateral manner, focusing on either mother, premature infant or nursing outcomes. No study has been found yet on measuring compliance with KC in order to improve the effectiveness of KC-EP according to weight gain, LOS, and breastfeeding rates at 3 months old for premature infants in Malaysia. Some of the studies also did not assess or report the adherence level to reflect the effectiveness of the intervention on outcomes.

Therefore, the focus of this study is aimed at introducing a KC-EP for mothers and nurses. The focus is on proper KC guidelines and protocols, and their benefits for the quality of care of premature infants. This is to enhance the effect of the KC-EP on mother and nursing outcomes. The study also aims to assess and explore mothers' and nurses' compliance rates in providing KC in order to make it a standardized and uniform practice in the NICU, which is then continued at home.

## **CHAPTER 3: METHODOLOGY**

### **3.1 Introduction**

This chapter sets out the research methods used to discuss the present research questions of this study. It provides a detailed overview of the research design, study setting, population

and sampling method, research instruments, collecting data procedures, and data analysis plan.

### **3.2 Research design and methodology**

Research is a systematic process aimed to identify the latest facts, ideas, or information and generate new findings about a specific phenomenon. Analysis methodology includes examining the assumptions, principles, and procedures of a specific investigative approach, and is characterized as the framework that applies to the whole research process (Cresswell, 2009). Research design is described as the total plan for acquiring or verifying new knowledge in such a way as to ensure that perhaps the answer(s) retrieved are relevant and truthful (Rebar, Gersch, Macnee & McCabe, 2011, p.175). The study design and methodology used in the present study are explained in the following sections below.

### **3.3 Study Design**

This is a quasi-experimental(QED), longitudinal design study to collect data on the effectiveness of a kangaroo care education programme (KC-EP) for mothers', nurses' and infants' outcomes. The QED is often described as a non-randomized, pre-post intervention study that is common in healthcare research when it is not logistically practicable or ethical to carry out a randomized control trial (Levin & Kate, 2007). This study met all four criteria of Harris, McGregor, Perencevich, Furuno, Zhu, Peterson, & Finkelstein (2006). Each reason is discussed below. In a human study, randomization in the intervention of known efficacy would not be allowed, unless the effectiveness is not known or doubtful. According to Jotzo, Martina & Christian (2005), psychological and mental support is required in critical circumstances, i.e. after premature birth. In the emotionally sensitive NICU environment, it seems unethical to provide some mothers with help, but other people oppose randomization for other reasons. A QED is an empirical instrument used to measure the causal effect of an

intervention on the basis of longitudinal evidence to decide whether the intervention has led to improvements in the outcomes of the target population. This study evaluated the effect of an educational programme on the outcomes of mothers, nurses, and preterm infants regarding KC techniques.

A QED design is considered an adequate technique for evaluating the causal and successful relationship between the independent and dependent variables found when a fully experimental or randomized control trial (RCT) design is not feasible (Harris et al., 2006). RCT is also not realistic for research into small-scale continuing education. Due to the aspect of non-random assignment to the control group or experimental group, a quasi-experimental research design was chosen as a multilevel intervention for the preterm infant. The experimental group participated in a structured training programme on evidence-based experience and skills: a KC-EP for mothers and nurses. The mother-infants dyad in the control group followed the standard unit practice, and both groups had homogeneous or similar characteristics.

### **3.3.1 Difficulty in randomizing the samples.**

The NICU is a critical and intensive care unit. Randomization of the samples will be difficult, as admission can not be predicted and samples fulfilling the requirements will be limited.

### **3.3.2 Difficulty of randomization by study setting**

The educational program can often not be randomized to individual environments because it is hard to prevent mothers from communicating with each other and from influencing the experimental groups, particularly if they are all in one ward. Thus data collection potentially masks the true effect.

### **3.3.3 Small available sample size**

For situations where only a limited sample size is necessary to assess the feasibility of an intervention, randomization may not be adequate to achieve equilibrium (Levin & Kate, 2006). Finding an alternative design, though, is easier.

### **3.6 Population and Sampling**

A population is a group of individuals to whom the researchers want to generalize their findings (Gay & Airasian, 2003). A population is also a group of people with unique characteristics which differentiate it from other groups (Cresswell, 2002; Kerlinger & Lee, 2000). The population was comprised of all mothers who had preterm infants admitted to the University Malaya Medical Center (UMMC), neonatal intensive care unit (NICU). Furthermore, the nurses were working in the NICU, UMMC. The population was estimated as stated below.

The UMMC, as a referral center, recorded an average of five thousand four hundred and ninety four (5494) mothers giving birth in 2011 and five thousand two hundred ninety eight (5298) in 2015, respectively (Table 3.1). The average number of premature infants admitted to UMMC was about 450 - 500 admissions yearly. For this study, the population was all mothers whose premature infants were admitted to the NICU at UMMC during the study period and they were recruited non-randomly based on infant admission days.

Table 3.1: Total Newborn Births and Total Premature Births at UMMC from 2011 To 2015

(Source: UMMC, Patient Information Management Section, Statistics Department, 2017)

Year	2011	2012	2013	2014	2015
Total births	5494	6275	6402	5497	5298
Total premature births	140	136	190	263	450
	(2.54%)	(2.16%)	(2.98%)	(4.78%)	(8.49%)

### **3.6.1 Target population**

A target population is the total collection of people from whom a sample could be taken (Ary, Donald, Jacobs, Lucy Cheser, Razavieh, Asghar, & Sorensen, 2010). The target population in this research was mothers whose preterm infant's corrected age was between 28 to < 36 + 6 gestational weeks, and also nurses working in the NICU, UMMC.

### **3.7 Criteria for sampling**

All mothers admitted to the NICU during the study period who had preterm infants were recruited according to the following criteria:

#### **3.7.1 Inclusion and exclusion criteria**

The decision to perform kangaroo care (KC) does not rely solely on the degree of neurodevelopment or postpartum age, but also on the stability of the infants. After birth, or within a few hours, days, or weeks, the baby can still be in an incubator or cradle as well as be clinically stable.

The selection of infants was based on the following criteria:

- premature infant at corrected age between 28 weeks to 36+6 weeks' gestation.
- infant clinically stable, eligible for KC, and admitted to the NICU.

The exclusion criteria for infants were:

- surgical infant i.e cleft lip, cleft palate, spina bifida, exomphalos and omphalocele.
- infant required medical treatment eg. prolonged phototherapy treatment.
- trisomy 21.

Mothers with preterm infants in the NICU who were able to perform the KC technique.

Therefore, the selection criteria for mothers were as follows:

- all mother-premature infants with corrected age between 28 to 36+6 weeks of gestation.
- mothers who were older than 18 years old and were able to give their consent.
- mothers who could speak and read either English or Malay.
- mother had no medical or surgical condition which required medication which interfered with breastfeeding and was eligible to perform KC for her preterm infant.

The exclusion criteria for mothers were:

- mothers who had previous premature infants.
- mother of quadruplets or more
- mother who had any medical and surgical conditions that required medication which interfered with breastfeeding and was not eligible to perform KC for her premature infant

Nurses also play a significant role in caring for mothers and babies during the maternal, perinatal and postnatal phases. They need to have expertise and confidence in their skills to provide neonatal treatment. The target group of nurses was registered nurses employed in UMMC's NICU. They were all invited to participate in this analysis to ensure the sample size was sufficient.

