### **1.7.4 Premature Infant**

According to Phillips, Goldstein, Hougland (2013), a baby born before 37 weeks of gestation (more than 3 weeks prior to the due date) is referred to as a preterm infant. In this study, a premature infant refers to an infant born alive earlier than usual, with a corrected age between 28 weeks to 36 + 6 weeks' gestation on its first admission to the NICU.

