### **1.7.11 Length of hospitalization stay (LOS)**

The Organization for Economic Co-operation and Development OECD (2020) reports that LOS is the total duration of time that patients spend in hospital. It is normally determined by the number of admissions or discharges divided by the number of days stayed by all hospitalized patients over a year. In this study, LOS relates to the number of days that the preterm infant spent in the hospital starting from the day of admission to the NICU until it

was allowed to be discharged or return home (in a day; 1 day = 24 hours); The length of NICU stays represents the number of days the premature infant spent in the intensive care unit recorded in days (1 day equals to 24 hours).

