### **3.13 When, Where and How Much Will KC-EP be Delivered**

The question "When" refers to the timing, in particular the best time for the intervention program to be implemented and the question "How much" refers to the intervention's intensity in terms of the amount, duration and period of time needed to implement the intervention (Feeley, Nancy, Zelkowitz, Phyllis, Shrier, Ian, 2011). Timing and strength are two important aspects to be considered in the implementation of a nursing intervention. The duration and strength of the KC-EP implementation were agreed upon after analysis of literature review findings regarding mothers who were slightly more depressed at the beginning of enrolment. In the first week, the mothers were less stressed (Tandberg et al., 2013), and in the week after birth and the week after discharge, the mothers were most stressed and worried (Gennaro, York, & Brooten, 1990).

In this study, 48 hours after the admission of the premature infant to the NICU, or after the clinical stabilization of the infant, the expected intervention program was started, and the mother was able to perform KC. Within 48 hours post-admission, a specific orientation (reinforcement) and the first meeting were conducted. The second set of data was collected at the premature infant's age of 1 month (44 weeks). The duration and frequency of KC-EP

implementation were based on the guidelines (USIKC, 2018). Moreover, the Guidelines on Kangaroo Care, which was published by WHO (2003), was derived from Davanzo, Brovedani, Travani, Kennedy, Crocetta, Sanesi, Strajn., & De Cunto (2013). The duration or frequency of KC-EP implementation was also based on the Bakermans-Kranenburg, Van IJzendoorn, and Juffer (2003) studies. Meta-analysis results from Bakermans-Kranenburg et al. (2003) found that the most effective intervention consisted of less than 16 sessions, and that less than 5 sessions ( $d=0.33$ ) were as effective as a 5-16 session intervention ( $d=0.36$ ). Accordingly, after consideration of these findings by Bakermans-Kranenburg et al. (2003) the expert panel decided in this study to limit the number of sessions to the minimum possible in practice.

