### 3.16.1 Data Collection Method for Mothers in the Control Group

Based on the day of the preterm infant's admission to the NICU, the researcher screened and recruited its mother into the control group. The mothers and premature infants were medically and surgically stable. The researchers chose mothers who were ready and returned after 48 hours to meet those who were interested to participate in the study. The selection was determined according to the mother's and premature infant's condition (clinically stable and eligible to perform KC), while the length of gestation had to be between 28 to 36/6 weeks. The study samples were selected from early February 2018 to the end of July 2018, within six months of the mothers in the control group. An average of two to four mothers was recruited per week. Mothers had to fill out a consent form. Consent was obtained from all mothers before they were recruited. The researchers contacted the participants in order to give an explanation of what was involved.

Questionnaire I for mothers was provided in an English and bahasa Melayu version. All mothers were given the same questionnaire in three phases ; T0, T1, and T2. At T0, all mothers were given the questionnaire on a voluntary basis to determine their perspectives on the implementation of KC as a baseline. The researchers created an identification code number for each of the mothers to be placed on the envelopes. Thus, mothers' answers could be matched for the T0, T1, and T2 questionnaires. The identification code started from MCG01 (mother control group 01). After a welcome speech and briefing (10 to 15 minutes), the questionnaires were given to the mothers to fill in and then collected. The mothers in the control group were also given a Kangaroo Care Progress Record (KCPR) booklet to record weight gain, feeding status, the routine practice of KC in the clinical setting and after discharge until 3 months old but without any information or input related to KC.

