### **3.16.2 Data Collection Method for Mothers in the Experimental Group**

The recruitment of the experimental group of mothers was based on premature infant's day of admission to the NICU after data collection from the nurses was completed. This was done to keep mothers in the experimental group from being exposed to the control group during their hospital stay. Both mothers and premature infants were medically and surgically stable, and mothers were willing to perform KC. For the experimental group of mothers, data collection was carried out over seven months from early October 2018 to the end of April 2019, after the nursing intervention program for nurses (KC-EP) had been completed. An average of two to four mothers was recruited per week.

The mother-infant dyads were recruited within 48 hours, as soon as they were clinically stable and eligible to perform KC. Samples were selected by the researcher, who returned after 48 hours to meet mothers interested in the study and agreed to complete the consent form. Prior to recruitment, consent was sought on a voluntary basis from all (n=48) mothers (Appendix B). The researchers explained to the mothers how to answer the questions (Questionnaire I) provided in English and Bahasa Malaysia. At T0, the questionnaire was given to all participants before the KC-EP was conducted. Each mother had her own identification code number put on the outside of the envelope to match Questionnaire I at T0, T1, and T2 accordingly. The identification numbers started from MEG01(mother experimental group 01).

In addition, signs of readiness to suckle, characterized by moving the tongue and mouth, and the desire for sucking, such as sucking fingers or mother's skin, were observed. As mentioned by Nyqvist (2012), early sucking competence is only observed from 29 weeks postpartum age onward, with the attainment of full breastfeeding as early as 32 weeks postpartum age. Those premature infants born before 32 weeks were given intravenous or nasogastric feeding.

The experimental group, comprised of mother-infant dyads, received a detailed verbal explanation on KC-EP. The contents of the module were verified by health care

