### **3.16.4 Method of Data Collection for Infants**

The researcher recruited the control group of premature infants first and then the experimental group after the nursing intervention program had been completed. The preterm infants in both groups were recruited based on infant admission days and according to mother-infant dyad condition. Firstly, all preterm infants between 28 and 36 + 6 days of gestation (n=48) were recruited by the researchers to participate in the study. The first

recruitment was assigned to the control group. The second recruitment of preterm infants who conformed to the inclusion criteria, i.e. clinically stable and ready to perform KC, was assigned to the experimental group (n=48) after written consent was given by their mothers. Those whose mothers refused to participate were excluded from the study. In the experimental group, data from the preterm infants were collected from the recruitment day until they reached 3 months old. A total of 48 newborn preterm infants from the same setting were given routine care (under servo-controlled radiant warmer or in a cradle with room heaters or blankets) and matched by corrected age. Feeding mode at admission to either group was monitored and jotted down, according to the route of feeding: tube feed, spoon-feed or breastfeeding. Before allocation to a group, it was ensured that the preterm infant was tolerating enteral feeds (over 24 hours) and had no regurgitation at age 28 to 36+6 day weeks of gestation. Corrected age was calculated using the Premature Baby Corrected Age Formula and classified between 28 to 36+6 days weeks of gestation. The baseline weight was calculated from the birth weight and weight on recruitment at T0, and outcome weight gain calculated from the weight on discharge, T1, and T2; this was recorded in the KCPR booklet provided. The body weight of the preterm infant was documented, after removing its clothes, using an electronic weighing scale with an accuracy of 5g at least 2 hours after the last feed and twice a week on Tuesdays and Saturdays according to the hospital protocol for weighing babies. Body weight was measured using a T- scale machine and recorded in grams (g).

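### Infant entry is anchored inconsistently and matching is on corrected age, while LOS counts from NICU admission, so unequal pre-enrolment stay could create or hide an LOS difference

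*Combined protocol and SAP*

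**What the plan says.** **Age criterion.** Section 3.7.1 requires a "premature infant at corrected age between 28 weeks to 36+6 weeks' gestation" and gives no time point; 3.6.1 uses the same range. The infant outcome subsection of 3.16.4, which covers Phases I and III together, ties that range to the day of recruitment. Section 1.7.4 defines the study infant as one "with a corrected age between 28 weeks to 36 + 6 weeks' gestation on its first admission to the NICU". Section 3.16.1, on the control group, says "while the length of gestation had to be between 28 to 36/6 weeks".

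**Timing.** For the experimental group, 3.16.2 says "The mother-infant dyads were recruited within 48 hours, as soon as they were clinically stable and eligible to perform KC", although the same paragraph has the researcher returning after 48 hours. Section 3.16.1 has control mothers met after 48 hours, with no upper limit. Section 3.13 starts the intervention "48 hours after the admission of the premature infant to the NICU, or after the clinical stabilization of the infant". Section 3.7.1 accepts that stability may be judged hours, days or weeks after birth. Section 3.16.4 also requires more than 24 hours of tolerated enteral feeds before allocation.

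**Matching and outcome.** Section 3.16.4 says the infants were "matched by corrected age". LOS is a primary outcome (3.9, Section B). Section 1.7.11 counts it "starting from the day of admission to the NICU until it" is allowed home.

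**Adjustment.** Gestational age at birth, birth weight and corrected age on recruitment are recorded (3.9, Section A). Section 3.16.4 lists gestation among the confounders, and 3.19.1 says covariance analysis corrects for potential confounders. The LOS row of Table 3.4 lists descriptive statistics, chi-square, GLM and a test, and names no covariate.

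**The concern.** The entry rules can select different infants. One admitted at birth at 24 weeks and now 28 weeks corrected meets a rule applied at recruitment, but fails one applied at first admission and a literal length-of-gestation rule. Section 3.4 says the unit handles infants from 22 weeks' gestation, so such admissions are plausible.

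Matching on corrected age does not repair this. Corrected age is gestation at birth plus time since birth, so two infants can agree on the sum and differ widely in both parts. Both parts feed into LOS counted from admission: the days already spent in the unit are in the total, and discharge depends partly on reaching a set weight (3.16.4). The arms are sequential and non-randomised, so nothing in the design equalises either part. A primary outcome could then differ between arms because of stay accrued before enrolment.

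**Working it through.** **The plan's own figure.** No sample size or power is given for LOS. The only calculation (3.7.2, weight gain) reproduces: 2 × 2.802² × 0.64 / 0.54² = 34.46, or 34.65 with the plan's rounding of 0.54² to 0.29. Either gives 35 per group, and 35/(1 − 0.30) = 50. This point does not depend on it. The analysed size is 48 per arm.

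**What matching leaves free.** Take two infants at 34 weeks corrected, each admitted at birth. One born at 34 weeks has 0 prior days; one born at 26 weeks has (34 − 26) × 7 = 56.

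**Range of pre-enrolment stay, by reading** (infant admitted at birth)
- 48-hour window binds: about 2 days.
- At least 28+0 at admission, enrolled up to 36+6: at most (36 × 7 + 6) − 28 × 7 = 62 days.
- Corrected age at recruitment only, born from 22+0: at most 258 − 154 = 104 days.

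Even the first-admission rule of 1.7.4 leaves a wide range unless a time limit also applies.

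**Shift in an arm's mean LOS.** Assume infants admitted at birth at 24 weeks and enrolled at 28 weeks: (28 − 24) × 7 = 28 days each.
- One extra infant: 28/48 = 0.58 days.
- Five extra infants (assumed; 5/48 is about 10% of an arm): 5 × 28/48 = 2.9 days.

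The KC effects cited in the literature review on LOS (section 2.4.3) are 20.7 − 16.6 = 4.1 days and 17.68 − 11.46 = 6.2 days.

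**Effect on the test.** Use a normal approximation, 48 per arm, two-sided 5%, with SE = SD × √(2/48). The documents give no LOS SD for this population. One cited study, in infants under 1500 g, gives √((4.32² + 8.64²)/2) = 6.8 days. SDs of 15 and 20 are added as assumptions. Chance of p < 0.05 with no KC effect:

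| Mean imbalance (days, assumed) | SD 6.8 | SD 15 | SD 20 |
|---|---|---|---|
| 2 | 30% | 10% | 8% |
| 3 | 58% | 17% | 11% |
| 5 | 95% | 37% | 23% |

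In the other direction, at SD 6.8 a true 4.1-day reduction has about 84% power with no imbalance. Power falls to about 33% with a 2-day opposing imbalance and about 12% with 3 days.

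A few very long stays would also widen the SD, so the SD 6.8 figures are the upper end of this illustration.

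**The case against.** The best defence is that the plan has a common anchor and knows the confounder. The outcome subsection of 3.16.4 ties corrected age to recruitment for both phases and agrees with 3.7.1. Gestation is listed as a confounder and covariance analysis is planned. This stands in part: a reader might infer that the plan makes no provision for gestation, and that is wrong. What is missing is a named covariate for LOS.

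Three other tempting inferences also fail.
- **A stricter gestation rule for controls.** The plan uses gestation and corrected age loosely; 3.7.1 combines both terms in one phrase. Section 3.16.1 may therefore be loose wording, and it is no evidence that the phases were screened differently.
- **Infants on early tube or intravenous feeding both due for recruitment and barred from it.** Section 3.16.2 allows intravenous or nasogastric feeding before 32 weeks. Nasogastric feeding is enteral and can meet the feeding condition.
- **Long pre-entry stays were usual.** Table 3.2(a) labels the admission day as week 28, 3.16.4 calls the routine-care infants newborn, and a binding 48-hour window leaves little room for bias. The unit also takes referrals, so an infant born early but first admitted later brings fewer pre-entry days.

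These points limit the likely size. They do not settle which time point or window governs, and loose wording does not explain admission against recruitment, or 48 hours against stabilisation.

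**Conclusion.** The inconsistency is in the text, and matching on corrected age cannot balance gestation at birth or stay already accrued. Where infants may enter days or weeks after admission, as 3.7.1 and 3.13 allow, LOS from admission includes days that KC could not have affected, and an imbalance in them could create or hide a difference.

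A reader might go further and conclude that the LOS comparison is biased. The documents do not support that: they give neither the number of infants born before 28 weeks nor the time from admission to recruitment by arm. The 2.9-day figure rests on an assumed excess of five infants, all admitted at birth at 24 weeks and enrolled at 28 weeks. With a binding 48-hour window the pre-entry stay is about 2 days and the problem is small. The point merits correction because the plan leaves the governing rule open for a primary outcome in non-randomised, sequential arms.

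**What to change.** 1. State one entry criterion with one time point, corrected age on the day of recruitment (as in 3.7.1 read with the outcome subsection of 3.16.4). Use it in 1.7.4, 3.6.1, 3.16.1 and 3.16.4 for both phases.
2. Have the sponsor reconcile the 48-hour and stabilisation passages (3.13, 3.14.1, 3.14.2, 3.16.1, 3.16.2). This review does not say which schedule is right.
3. Do not rely on matching by corrected age. In Table 3.4, specify the LOS comparison as a covariance analysis adjusted for gestational age at birth and birth weight.
4. Report LOS from the actual recruitment date to discharge beside LOS from admission. Use the actual date rather than a first day of eligibility, which is not among the listed variables and would rest on unblinded judgement.
5. Report gestational age at birth and days from admission to recruitment by arm.

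**Cost.** Wording changes and a little more analysis. Both covariates and the admission and discharge dates are already recorded. Section 3.9 lists corrected age on recruitment in weeks rather than a recruitment date, so the date may have to come from the first dated progress-booklet entry. LOS from recruitment is less comparable with studies that count from admission, which is why both are reported.
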